#### **6.10. Urine Samples**

Urine collection for the following laboratory analyses:

- Urinalysis (all visits)
- Urine chemistry (all visits)
- Renal safety evaluations: Fasting (no food or drink, except water, at least 8 hours prior to blood collection) retinol binding protein and beta-2 microglobulin (Day 1, Weeks 4, 12, 24, 48, 60, 72, 84, and 96). Renal safety evaluations will not be done after Week 96.

#### **6.11. Blood and Urine Sample Storage**

Residual blood and urine samples taken throughout the study (including the post Week 96 extension phase) will be stored. Stored samples may be used by the Sponsor or its research partners to help answer questions about the study drug, and HIV disease and its associated conditions, or to provide additional safety data. These samples will be stored until the completion of all visits for all subjects and the final study analysis.

#### **6.12. Virologic Failure**

Virologic failure is defined as confirmed virologic rebound of HIV-1 RNA  $\geq 50$  copies/mL at 2 consecutive visits, or having HIV-1 RNA  $\geq 50$  copies/mL at study drug discontinuation or at Week 48, Week 72 or Week 96.

##### **6.12.1. Management of Virologic Rebound**

Subjects who meet the criteria listed below will be considered to have virologic rebound:

- At any post Day 1 visit, a rebound in HIV-1 RNA  $\geq 50$  copies/mL

Following the virologic rebound, subjects will be asked to return to the clinic for a scheduled or unscheduled blood draw (within 2-3 weeks after the date of the original test that resulted in HIV-1 RNA  $\geq 50$  copies/mL). Subjects with HIV-1 RNA values between 50-200 copies/mL should follow the algorithm in Figure 6-1. If virologic rebound is confirmed at the scheduled or unscheduled visit and the HIV-1 RNA is  $\geq 200$  copies/mL, the plasma sample from the confirmation visit will be the primary sample used for HIV-1 genotypic and phenotypic testing.

After a subject's first post-Day 1 resistance test, additional testing will be conducted on a case-by-case basis. Any subject may be discontinued at Investigator's discretion or per local treatment guidelines.

[figure not shown]
If no resistance to study drugs is detected from the genotype or phenotype, the subject may remain on study drugs and HIV-1 RNA test should be analyzed at a new visit (within 2-3 weeks after date of test with HIV-1 RNA  $\geq$  50 copies/mL). Investigators should carefully evaluate the benefits and risks of remaining on study drug for each individual subject and document this assessment in the on-site medical record.

Subjects who are noncompliant on an ongoing basis will be considered for discontinuation per the Investigator's discretion or local treatment guidelines. Investigators who opt to discontinue study drugs for an individual subject must discuss with the Medical Monitor prior to study drug discontinuation.

For subjects who are off study drug but remain on study, it will be the Investigator's discretion to manage virologic rebound.

Please refer to [Figure 6-1](#) for the management of subjects who meet the criteria for virologic rebound.

**Figure 6-1. Virologic Rebound Schema**

a If the HIV-1 RNA is between 50 and 200 copies/mL, a reflex HIV-1 RNA repeat test will be conducted on stored plasma if available. If the repeat result is < 50 copies/mL, then no further action is required. If the repeat result is ≥ 50 copies/mL then proceed to the scheduled or unscheduled visit 2 – 3 weeks later.

b If the HIV-1 RNA is < 50 copies/mL then no further action is required. If the HIV-1 RNA is between 50 and 200 copies/mL, a reflex HIV-1 RNA repeat test will be conducted on stored plasma if available. If the repeat result is < 50 copies/mL, then no further action is required. If the repeat result is between 50 and 200 copies/mL this is protocol defined confirmed virologic failure and the Medical Monitor should be consulted. If the repeat result is ≥ 200 copies/mL, then a Genotype and Phenotype test will be ordered.

c If virologic rebound is confirmed and the last HIV-1 RNA is ≥ 200 copies/mL, the HIV-1 genotype and phenotype (reverse transcriptase, protease and integrase) will be analyzed. If the genotype and phenotype assay fails, Investigator reviews study drug continuation/discontinuation options and discuss with the Medical Monitor prior to study drug discontinuation.

d If no resistance to study drug is detected, HIV-1 RNA will be repeated 2 – 3 weeks later. Investigator reviews study drug continuation/discontinuation options and discuss with the Medical Monitor prior to study drug discontinuation. The subject will remain in the study.

e A new ARV regimen will be configured, at the Investigator’s discretion and the subject will remain in the study.

**6.12.2. Subjects with HIV-1 RNA  $\geq$  50 copies/mL at Study Drug Discontinuation or at Week 48, Week 72 or Week 96**

Subjects with HIV-1 RNA  $\geq$  50 copies/mL at study drug discontinuation or last visit will be considered virologic failures. Subjects with HIV-1 RNA  $\geq$  50 copies/mL at Weeks 48, 72 or 96 will be asked to return for an unscheduled visit within the visit window for a retest.

Subjects with HIV-1 RNA  $\geq$  200 copies/mL at study drug discontinuation, last visit, or last measurement in the Weeks 48, 72 or 96 window, will also have resistance testing conducted.

## 7. ADVERSE EVENTS AND TOXICITY MANAGEMENT

### 7.1. Definitions of Adverse Events, Adverse Reactions, and Serious Adverse Events

#### 7.1.1. Adverse Events

An adverse event (AE) is any untoward medical occurrence in a clinical study subject administered a medicinal product, which does not necessarily have a causal relationship with the treatment. An AE can therefore be any unfavorable and/or unintended sign, symptom, or disease temporally associated with the use of a medicinal product, whether or not considered related to the medicinal product. AEs may also include pre- or post-treatment complications that occur as a result of protocol specified procedures, lack of efficacy, overdose, drug abuse/misuse reports, or occupational exposure. Preexisting events that increase in severity or change in nature during or as a consequence of participation in the clinical study will also be considered AEs.

An AE does not include the following:

- Medical or surgical procedures such as surgery, endoscopy, tooth extraction, and transfusion. The condition that led to the procedure may be an adverse event and must be reported.
- Pre-existing diseases, conditions, or laboratory abnormalities present or detected before the screening visit that do not worsen
- Situations where an untoward medical occurrence has not occurred (e.g., hospitalization for elective surgery, social and/or convenience admissions)
- Overdose without clinical sequelae
- Any medical condition or clinically significant laboratory abnormality with an onset date before the consent form is signed and not related to a protocol-associated procedure is not an AE. It is considered to be pre-existing and should be documented on the medical history CRF.

#### 7.1.2. Serious Adverse Events

A **serious adverse event** (SAE) is defined as an event that, at any dose, results in the following:

- Death
- Life-threatening (Note: The term “life-threatening” in the definition of “serious” refers to an event in which the subject was at risk of death at the time of the event; it does not refer to an event that hypothetically might have caused death if it were more severe.)
- In-patient hospitalization or prolongation of existing hospitalization

- Persistent or significant disability/incapacity
- A congenital anomaly/birth defect
- A medically important event or reaction: such events may not be immediately life-threatening or result in death or hospitalization but may jeopardize the subject or may require intervention to prevent one of the other outcomes constituting SAEs. Medical and scientific judgment must be exercised to determine whether such an event is a reportable under expedited reporting rules. Examples of medically important events include intensive treatment in an emergency room or at home for allergic bronchospasm; blood dyscrasias or convulsions that do not result in hospitalization; and development of drug dependency or drug abuse. For the avoidance of doubt, infections resulting from contaminated medicinal product will be considered a medically important event and subject to expedited reporting requirements.

### 7.1.3. Assessment of Causality for Study Drugs and Procedures

The investigator or qualified subinvestigator is responsible for assessing the relationship to IMP therapy using clinical judgment and the following considerations:

- **No:** Evidence exists that the adverse event has an etiology other than the IMP. For SAEs, an alternative causality must be provided (e.g., pre-existing condition, underlying disease, intercurrent illness, or concomitant medication).
- **Yes:** There is reasonable possibility that the event may have been caused by the investigational medicinal product.

It should be emphasized that ineffective treatment should not be considered as causally related in the context of adverse event reporting.

The relationship to study procedures (e.g., invasive procedures such as venipuncture or biopsy) should be assessed using the following considerations:

- **No:** Evidence exists that the adverse event has an etiology other than the study procedure.
- **Yes:** The adverse event occurred as a result of protocol procedures, (e.g., venipuncture)

### 7.1.4. Assessment of Severity

AE severity should be recorded and graded according to the Gilead Grading Scale for Severity of Adverse Events and Laboratory Abnormalities ([Appendix 4](#)). For adverse events associated with laboratory abnormalities, the event should be graded on the basis of the clinical severity in the context of the underlying conditions; this may or may not be in agreement with the grading of the laboratory abnormality.

The distinction between the seriousness and the severity of an adverse event should be noted.

Severe is a measure of intensity; thus, a severe reaction is not necessarily a serious reaction. For example, a headache may be severe in intensity, but would not be classified as serious unless it met one of the criteria for serious events.

## **7.2. Investigator Requirements and Instructions for Reporting Adverse Events and Serious Adverse Events to Gilead**

Requirements for collection prior to study drug initiation:

After informed consent, but prior to initiation of study medication, the following types of events should be reported on the eCRF: all SAEs and adverse events related to protocol-mandated procedures.

### **7.2.1. Adverse Events**

Following initiation of study medication, collect all AEs, regardless of cause or relationship, until 30-days after last administration of study IMP must be reported to the eCRF database as instructed.

All AEs should be followed up until resolution or until the adverse event is stable, if possible. Gilead Sciences may request that certain AEs be followed beyond the protocol defined follow up period.

### **7.2.2. Serious Adverse Events**

All SAEs, regardless of cause or relationship, that occurs after the subject first consents to participate in the study (ie, signing the informed consent) and throughout the duration of the study, including the protocol-required post treatment follow-up period, must be reported to the eCRF database and Gilead Pharmacovigilance and Epidemiology (PV&E) as instructed. This also includes any SAEs resulting from protocol-associated procedures performed after informed consent is signed.

Any SAEs and deaths that occur after the post treatment follow-up visit but within 30-days of the last dose of study IMP, regardless of causality, should also be reported.

Investigators are not obligated to actively seek SAEs after the protocol defined follow up period ; however, if the investigator learns of any SAEs that occur after study participation has concluded and the event is deemed relevant to the use of IMP, he/she should promptly document and report the event to Gilead PV&E.

#### Electronic Serious Adverse Event (eSAE) Reporting Process

- Site personnel record all SAE data in the eCRF database and from there transmit the SAE information to Gilead PV&E within 24 hours of the investigator's knowledge of the event. Detailed instructions can be found in the eCRF completion guidelines.

- If it is not possible to record and submit the SAE information electronically, because the eCRF database cannot be accessed or is not available (including at study start), record the SAE on the paper serious adverse event report form and submit by e-mail or fax within 24 hours of the investigator's knowledge of the event to:

Gilead PV&E:

Fax: PPD

E-mail: PPD

- As soon as it is possible to do so, any SAE reported via paper must be transcribed into the eCRF Database according to instructions in the eCRF completion guidelines.
- If an SAE has been reported via a paper form because the eCRF database has been locked, no further action is necessary.
- All AEs and SAEs will be recorded in the eCRF database within the timelines outlined in the eCRF completion guideline.
- For fatal or life-threatening events, copies of hospital case reports, autopsy reports, and other documents are also to be submitted by e-mail or fax when requested and applicable. Transmission of such documents should occur without personal subject identification, maintaining the traceability of a document to the subject identifiers.
- Additional information may be requested to ensure the timely completion of accurate safety reports.
- Any medications necessary for treatment of the SAE must be recorded onto the concomitant medication section of the subject's CRF and the event description section of the SAE form.

### 7.3. Gilead Reporting Requirements

Depending on relevant local legislation or regulations, including the applicable US FDA Code of Federal Regulations, the EU Clinical Trials Directive (2001/20/EC) and relevant updates, and other country-specific legislation or regulations, Gilead may be required to expedite to worldwide regulatory agencies reports of SAEs, serious adverse drug reactions (SADRs), or suspected unexpected serious adverse reactions (SUSARs). In accordance with the EU Clinical Trials Directive (2001/20/EC), Gilead or a specified designee will notify worldwide regulatory agencies and the relevant IEC in concerned Member States of applicable SUSARs as outlined in current regulations.

Assessment of expectedness for SAEs will be determined by Gilead using reference safety information specified in the investigator's brochure or relevant local label as applicable.

All investigators will receive a safety letter notifying them of relevant SUSAR reports associated with any study IMP. The investigator should notify the IRB or IEC of SUSAR reports as soon as is practical, where this is required by local regulatory agencies, and in accordance with the local institutional policy.

#### **7.4. Toxicity Management**

All clinical and clinically significant laboratory toxicities will be managed according to uniform guidelines detailed in [Appendix 3](#), and as outlined below.

Refer to Section 6.6, Criteria for Study Drug Interruption or Discontinuation, for additional specific discontinuation criteria. For Specific toxicity discontinuation criteria please refer to Section 7.4. The Gilead Medical Monitor should be consulted prior to study drug discontinuation when medically feasible.

##### **7.4.1. Grades 1 and 2 Laboratory Abnormality or Clinical Event**

Continue study drug at the discretion of the investigator.

##### **7.4.2. Grades 3 Laboratory Abnormality or Clinical Event**

- For a Grade 3 clinically significant laboratory abnormality or clinical event, IMP may be continued if the event is considered to be unrelated to IMP.
- For a Grade 3 clinical event, or clinically significant laboratory abnormality confirmed by repeat testing, that is considered to be related to IMP, IMP should be withheld until the toxicity returns to  $\leq$  Grade 2.
- If a laboratory abnormality recurs to  $\geq$  Grade 3 following re-challenge with IMP and is considered related to IMP, then IMP should be permanently discontinued and the subject managed according to local practice. Recurrence of laboratory abnormalities considered unrelated to IMP may not require permanent discontinuation.

##### **7.4.3. Grade 4 Laboratory Abnormality or Clinical Event**

For a Grade 4 clinical event or clinically significant Grade 4 laboratory abnormality that is considered related to IMP, IMP should be permanently discontinued and the subject managed according to local practice. The subject should be followed as clinically indicated until the laboratory abnormality returns to baseline or is otherwise explained, whichever occurs first.

Investigational medicinal product may be continued without dose interruption for a clinically non-significant Grade 4 laboratory abnormality (e.g., Grade 4 creatine kinase [CK] after strenuous exercise or triglyceride elevation that is nonfasting or that can be medically managed)

Treatment-emergent toxicities will be noted by the investigator and brought to the attention of the Gilead medical monitor, who will have a discussion with the investigator and decide the appropriate course of action. Whether or not considered treatment-related, all subjects experiencing AEs must be monitored periodically until symptoms subside, any abnormal laboratory values have resolved or returned to baseline levels or they are considered irreversible, or until there is a satisfactory explanation for the changes observed.

Any questions regarding toxicity management should be directed to the Gilead Medical Monitor.

#### **7.4.4. On-Treatment ALT Flare and Post-Treatment Exacerbation of Hepatitis B Management**

A On-Treatment ALT Flare is defined as:

- Confirmed (within 3 days of receipt of initial laboratory results) serum ALT  $> 2 \times$  Day 1 value and  $> 10 \times$  ULN, with or without associated symptoms

##### **7.4.4.1. Management of ALT Flare in Subjects Receiving Study Medication**

If laboratory results indicate elevation of ALT  $> 2 \times$  Day 1 value and  $> 10 \times$  ULN, the following is recommended:

- Schedule the subject to return to the clinic as soon as possible (ideally within 3 days after initial laboratory results were drawn). During the visit, a clinical assessment of the subject will be performed. The assessment should include a physical examination and evaluation of the subject's mental status.
- If the ALT elevation is confirmed, request the central clinical laboratory to conduct reflex testing for plasma HBV DNA, HBV serology (HBsAg and HBsAb), HDV, HAV IgM, and HCV serology

Check the following laboratory parameters: serum ALT and AST, total bilirubin, INR, and serum albumin. Based on the results of the confirmatory tests, the following treatment modifications are recommended:

##### **Elevated Liver Enzymes, Normal or Stable relative to Day 1 Liver Function Tests**

If ALT levels are elevated (i.e.,  $> 2 \times$  Day 1 and  $> 10 \times$  ULN) with normal or stable total bilirubin and INR relative to Day 1, the subject may remain on study medication and should be monitored weekly as long as ALT levels return to normal or Day 1 level. During monitoring, if the ALT values remain persistently elevated, the Investigator should discuss with the Gilead Medical Monitor whether the study drug should be discontinued.

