##### **Elevated Liver Enzymes, Elevated Liver Function Tests**

If ALT values are elevated (i.e.,  $> 2 \times$  Day 1 and  $> 10 \times$  ULN), and total bilirubin is confirmed to be  $2 \times$  Day 1 value, and INR is 0.5 above Day 1, provided both are  $>$  ULN, the investigator should consider discontinuing study medication (upon discussion with the Gilead Medical Monitor, unless the safety of the patient is of immediate concern). The subject should be monitored weekly as long as ALT, total bilirubin, and INR values remain elevated or above Day 1 values.

During monitoring, if the ALT values and the liver function tests remain persistently elevated, the Investigator should discuss with the Gilead Medical Monitor whether the study drug should be discontinued.

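### For a confirmed, clinically significant, drug-related ALT above 10 x ULN, Protocol 7.4.3 says stop permanently while 7.4.4.1 lets the subject continue or only consider stopping, and no readable text says which governs

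*Protocol*

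**What the plan says.** Protocol 7.4.3 gives the general rule for Grade 4. When a clinical event, or a clinically significant laboratory value, of that grade is "considered related to IMP, IMP should be permanently discontinued and the subject managed according to local practice". Its only exception is for laboratory abnormalities that are not clinically significant. It also brings treatment-emergent toxicities to the Medical Monitor, "who will have a discussion with the investigator and decide the appropriate course of action".

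Protocol 7.4.4 defines an on-treatment ALT flare as a confirmed ALT above both 2 x Day 1 and 10 x ULN, with or without symptoms. Section 7.4.4.1 then states: "Based on the results of the confirmatory tests, the following treatment modifications are recommended". Two branches follow.

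- **Bilirubin and INR normal or stable:** "with normal or stable total bilirubin and INR relative to Day 1, the subject may remain on study medication", with weekly monitoring. If ALT stays high, stopping is discussed with the Medical Monitor.
- **Bilirubin 2 x Day 1** "and INR is 0.5 above Day 1, provided both are" **above ULN:** "the investigator should consider discontinuing study medication (upon discussion with the Gilead Medical Monitor, unless the safety of the patient is of immediate concern".

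Neither branch mentions relatedness to study drug or hepatitis B status.

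The opening of 7.4 refers to Appendix 3 as well as to the subsections, without an order of precedence. Only the heading of Appendix 3 is readable in the text available.

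**The concern.** A site with a clinically significant ALT above 10 x ULN that it attributes to study drug finds two instructions. One is to stop for good. The other, depending on bilirubin and INR, is that the subject may continue or that stopping should be considered. A reader who lets the more specific section govern would keep a related Grade 4 ALT on drug. A reader who lets the firmer wording govern would stop.

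The stake is patient safety. Section 7.4.5 calls the human risk of the monkey hepatobiliary findings unknown at the clinical dose, and the risk/benefit assessment in 1.7 relies on the guidance in 7.4 to manage it. That guidance should give one answer for a marked liver signal.

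**Working it through.** The plan states no figure to reproduce. The check is whether one patient can fall under both rules, and whether other text then resolves the overlap.

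**Inputs**

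- Grade 4 ALT: above 10 x ULN (Appendix 4, Enzymes).
- Flare: confirmed ALT above 2 x Day 1 and above 10 x ULN (7.4.4).
- Entry cap: ALT at most 5 x ULN (inclusion criterion 12).

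**Step 1: do the thresholds coincide?** The flare cut-off is the larger of 10 x ULN and 2 x Day 1. At the entry cap, 2 x 5 = 10, so with Day 1 ALT at or below 5 x ULN the Day 1 condition adds nothing. Every confirmed Grade 4 ALT is then a flare. If Day 1 ALT had risen to 6 x ULN after screening, the flare cut-off would be 2 x 6 = 12 x ULN, and a value between 10 and 12 x ULN would fall under 7.4.3 alone. In all cases a flare is Grade 4.

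**Step 2: what does each section say for a confirmed flare that is clinically significant and considered related?**

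| Bilirubin and INR | 7.4.3 | 7.4.4.1 | Conflict |
|---|---|---|---|
| Both normal or stable | Stop permanently | May continue, weekly monitoring | Yes |
| Bilirubin 2 x Day 1 and INR 0.5 above Day 1, both above ULN | Stop permanently | Consider stopping | Yes, weaker |
| Any other pattern (one raised, or intermediate rises) | Stop permanently | No initial advice on drug | No |

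Flares that are unrelated or not clinically significant do not meet the 7.4.3 stopping rule, so they raise no conflict.

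**Step 3: does other text set precedence?**

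- The 7.4.3 exception covers only values that are not clinically significant.
- The opening of 7.4 sends the reader to Section 7.4 itself for specific discontinuation criteria.
- 7.4.5 requires prompt contact with the Medical Monitor and refers back to 7.4 for graded abnormalities.
- Section 6.6 (unacceptable toxicity) rests on judgment.
- SAP 7.2.4 lists flares only for subjects with HIV/HBV coinfection. That is a reporting rule and does not restrict clinical management.
- Appendix 3 cannot be assessed.

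The overlap therefore exists, and the readable text does not resolve it.

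**The case against.** The strongest reply is that both sections can be obeyed together. Section 7.4.3 uses firm wording for related, significant events; 7.4.4.1 gives a permission within recommended modifications. A natural reading is sequential: work the flare up under 7.4.4.1, then apply 7.4.3 once it is judged related. The heading of 7.4.4, the viral reflex tests and the SAP listing all point to viral flare as the intended subject. The Medical Monitor is named as decision-maker, and 7.4.3 sends any toxicity question there.

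Much of this stands. A site that stops drug breaches neither section, and someone is available to ask. But the sequential reading and the viral purpose are inferences that the text does not state, and case-by-case consultation is not a rule of precedence. Appendix 3 may contain such a rule; its content being unreadable here is not evidence that the plan lacks one.

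Two stronger readings go too far.

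- **That the protocol treats a worse liver signal more leniently.** For a confirmed related Grade 3 value, 7.4.2 says "IMP should be withheld until the toxicity returns to" Grade 2 or lower, and for a laboratory abnormality that recurs to Grade 3 or above "following re-challenge with IMP and is considered related to IMP, then IMP should be permanently discontinued". A reader might infer that a related ALT of 9 x ULN is withheld while one of 11 x ULN continues. That inversion appears only if 7.4.4.1 is taken to override 7.4.3, which the protocol does not say.
- **That the number of affected subjects can be bounded.** The phase 2 summary in Protocol 1.2.3.3 reports no Grade 4 ALT through Week 24. Those subjects were ART-naive and took bictegravir 75 mg. Twenty-four weeks of such data give no ceiling for a 96-week study of switched subjects aged 65 or over, and the documents do not say what share of elevations would be judged related.

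**Conclusion.** The point holds in limited form. For a confirmed ALT above 10 x ULN and above 2 x Day 1, clinically significant and considered related, 7.4.3 and 7.4.4.1 differ in two situations: stop versus may continue, and stop versus consider stopping. No readable text says which prevails.

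The size is small. Section 1.7 reports no liver or bile duct adverse drug reactions identified in humans on bictegravir, events should be rare, the Medical Monitor is involved, and no efficacy estimate changes. The documents do not support a claim that subjects would in fact be kept on drug unsafely. The conclusion assumes that Appendix 3 contains no precedence rule, which needs checking. It is best classed as a cheap improvement to patient safety.

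**What to change.** Add to 7.4.4.1:

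> The options to continue with weekly monitoring or to consider discontinuation apply to flares attributed to viral hepatitis (including HBV flare or immune reconstitution) or otherwise not considered related to IMP. A confirmed, clinically significant ALT >10 x ULN considered related to IMP, without such a viral cause, follows Section 7.4.3. In HBV-coinfected subjects, consult the Medical Monitor before stopping unless safety is of immediate concern, and manage under 7.4.4.2 after stopping.

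Cross-reference this in 7.4.3 and confirm that Appendix 3 agrees.

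The viral clause is needed. Section 1.7 lists immune reconstitution as a potential risk of antiretrovirals, so a viral flare could be judged drug-related. A bare relatedness test would then force permanent discontinuation in a coinfected subject, with the post-treatment exacerbation risk that 7.4.4.2 addresses.

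The cost is a short protocol clarification and slightly less investigator discretion, with no new procedures or data. It helps only while subjects are on drug.
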